### **10.3.3 Safety Population**

- All patients who were randomized and applied at least one dose of the study product.

## **10.4 Baseline Comparability**

Baseline comparability of all treatment groups will be evaluated separately in the ITT, PP and Safety populations. Comparative analyses will use appropriate statistical tests (e.g., one-way analysis of variance, Cochran-Mantel-Haenszel Test).

The following baseline demographics (determined from their initial study visit) will be evaluated:

- Age (years)
- Gender (male/female)
- Ethnicity (Hispanic/non Hispanic)
- Race (White, Black/African American, Native Hawaiian or Other Pacific Islander, Asian, American Indian or Alaska Native, Other)
- Baseline total BSA
- Baseline % BSA affected with psoriasis
- IGA score
- TLSS Score
- PASI Score
- Target Lesion size (area)

Descriptive statistics by treatment group will be presented.

## **10.5 Efficacy Endpoints**

### **Primary Efficacy Endpoints**

## **CONFIDENTIAL PROTOCOL**

A Randomized, Double-Blind, Placebo-Controlled, Parallel-Design, Multiple-Site Clinical Study to Evaluate the Efficacy and Safety of Desoximetasone Topical Spray, 0.15% (Taro Pharmaceuticals, U.S.A., Inc.) in Patients with Mild to Moderate Plaque Psoriasis

---

1. The proportion of patients in each treatment group who are considered a Clinical Success at Day  $28 \pm 2$  (i.e., at least a 2-grade improvement from the patient's baseline IGA score).
2. The proportion of patients in each treatment group who are considered a Treatment Success for the Target Lesion at Day  $28 \pm 2$  (i.e., a TLSS value of 0 or 1 at Day  $28 \pm 2$  for each of the three signs and symptoms (i.e., erythema, scaling and plaque elevation) depending on the patient's baseline TLSS).

### **Definitions:**

1. Treatment Success: To be considered a Treatment Success the patient's TLSS value at Day  $28 \pm 2$  must be 0 if their baseline TLSS value is 2 and must be 0 or 1 if their baseline TLSS value is  $> 2$  for each of the individual signs and symptoms
2. Treatment Failure: A patient will be considered a Treatment Failure if:
  - a. the patient's TLSS value is  $> 0$  if their baseline TLSS value is 2 or  $> 1$  if their baseline IGA score is  $> 2$  for any of the individual signs and symptoms
  - b. the patient was considered to have an insufficient therapeutic response
3. Clinical Success: To be considered a Clinical Success the patient must have at least a 2-grade improvement from their baseline IGA score. That is, an IGA score of 0 at Day  $28 \pm 2$  if their baseline IGA score is 2 or an IGA score of 0 or 1 at Day  $28 \pm 2$  if their baseline IGA score is 3
4. Clinical Failure: A patient will be considered a Clinical Failure if:
  - a. the patient's IGA score is  $> 0$  if the baseline IGA score is 2 or  $> 1$  if the baseline IGA score is 3
  - b. the patient was considered to have an insufficient therapeutic response

### **Secondary Efficacy Endpoints**

The secondary efficacy endpoints are:

1. The proportion of patients with a baseline IGA score of 3 who are considered a Clinical Success.
2. The proportion of patients with a baseline IGA score of 3 who are considered a Treatment Success.
3. The proportion of patients with a baseline IGA score of 2 who are considered a Clinical Success.
4. The proportion of patients with a baseline IGA score of 2 who are considered a Treatment Success.
5. The change from baseline in %BSA affected at Day  $28 \pm 2$  will be evaluated as a secondary endpoint.

## **CONFIDENTIAL PROTOCOL**

A Randomized, Double-Blind, Placebo-Controlled, Parallel-Design, Multiple-Site Clinical Study to Evaluate the Efficacy and Safety of Desoximetasone Topical Spray, 0.15% (Taro Pharmaceuticals, U.S.A., Inc.) in Patients with Mild to Moderate Plaque Psoriasis

---

### **10.6 Primary Efficacy Analyses**

The Test treatment will be compared with Placebo for each primary endpoint at the 5% significance level ( $p < 0.05$ ; two-sided, Cochran-Mantel-Haenszel exact test) in the ITT population using last observation carried forward (LOCF). Superiority of Test over Placebo will be demonstrated if both dichotomous endpoints show statistical significance at the 5% significance level.

For sensitivity testing, the primary analysis will also be performed using the PP population.

### **10.7 Secondary Efficacy Analyses**

The Test treatment will be compared with Placebo for each dichotomous secondary endpoint at the 5% significance level ( $p < 0.05$ ; two-sided, Cochran-Mantel-Haenszel exact test) in the ITT population using LOCF.

The Test treatment will be compared with Placebo for the continuous secondary endpoint at the 5% significance level in the ITT population using LOCF. Analysis of Covariance (ANCOVA) with treatment and site as fixed effects and baseline %BSA as a covariate in the model will be used for the evaluation of the continuous secondary endpoint.

For the secondary efficacy analyses, superiority of Test over Placebo will be considered supported for each endpoint if the difference is statistically significantly greater than 0 at the 5% significance level. There will be no multiplicity adjustment for the evaluation of the five secondary endpoints.

Descriptive statistical analysis will be generated to compare the efficacy results in each treatment group at each visit.

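### Section 10.7 lets superiority be called supported on any of five secondary endpoints at an unadjusted 5%, without requiring the co-primary rule of 10.6 to be met

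*Protocol*

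**What the plan says.** Protocol 10.6 sets the rule for the overall claim: "Superiority of Test over Placebo will be demonstrated if both dichotomous endpoints show statistical significance at the 5% significance level".

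Protocol 10.7 sets a separate rule for the secondaries. For the four binary endpoints: "The Test treatment will be compared with Placebo for each dichotomous secondary endpoint at the 5% significance level", using a "two-sided, Cochran-Mantel-Haenszel exact test". For change in %BSA: "The Test treatment will be compared with Placebo for the continuous secondary endpoint at the 5% significance level in the ITT population using LOCF". The decision rule is that "superiority of Test over Placebo will be considered supported for each endpoint if the difference is statistically significantly greater than 0" at the 5% level, followed by "There will be no multiplicity adjustment for the evaluation of the five secondary endpoints". The synopsis repeats the decision rule and the no-adjustment sentence.

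The list in 10.5 shows what is tested. Endpoint 1 is "The proportion of patients with a baseline IGA score of 3 who are considered a Clinical Success" and endpoint 4 is "The proportion of patients with a baseline IGA score of 2 who are considered a Treatment Success". Endpoints 2 and 3 are the other two combinations of outcome and IGA stratum, and endpoint 5 is change in %BSA. Eligibility admits only baseline IGA 2 or 3, so the two strata together make up the whole trial.

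**The concern.** Leaving secondary endpoints unadjusted is common and defensible when they are descriptive. Here they are not labelled descriptive, exploratory or nominal. Each has a decision rule whose output is a superiority statement.

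Four of the five also put the primary question again to the same patients under a looser standard. Section 10.6 requires both outcomes to be significant in the whole trial, whereas 10.7 is satisfied endpoint by endpoint by either outcome in either stratum. No sentence in 10.6, 10.7 or the synopsis makes the second rule conditional on the first. A report of a trial that failed 10.6 could therefore say, within its protocol, that superiority was supported in moderate or in mild patients, or on %BSA. No error rate is set for such statements taken together.

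**Working it through.** **Inputs from the protocol.** Five secondary tests, each at two-sided 5% (10.7), so 0.025 in the direction favouring Test. Up to 60 patients per arm enrolled and 50 evaluable per arm; 40% success on Test and 12% on vehicle; 100% correlation assumed between Clinical and Treatment Success (10.2).

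**Assumptions (not in the protocol).** An even IGA split, giving 30 per arm per stratum; latent correlations between the two outcomes below 1; a %BSA test independent of the binary tests; Fisher's exact test standing in for the exact CMH test.

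**The plan's own figure.** For 40% v 12% with 50 per arm and a pooled Z-test, the mean rate is 0.26:

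- z = (0.28·√50 − 1.96·√(2·0.26·0.74)) / √(0.40·0.60 + 0.12·0.88) = (1.980 − 1.216) / 0.588 = 1.30
- Power = Φ(1.30) = 90.3%. Fisher's exact test gives 87.2%. The stated 89% is reproduced within 2 points.

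**Outer bounds with no true effect.**

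- Five independent full-level tests, at least one favouring Test: 1 − 0.975⁵ = 11.9%.
- The two outcomes fully correlated within each stratum (three effective tests): 1 − 0.975³ = 7.3%.

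**Exact tests with no true effect, 30 per arm per stratum.** Simulation gives the chance that at least one of the four subgroup tests favours Test. The independent %BSA test is then added as 1 − (1 − a)·0.975.

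| Response rate, both arms | Latent correlation | Any of four subgroup tests (a) | Any of five |
|---|---|---|---|
| 12% | 0.5 | 2.4% | 1 − 0.976·0.975 = 4.8% |
| 12% | near 1 | 1.9% | 1 − 0.981·0.975 = 4.4% |
| 40% | 0.5 | 5.0% | 1 − 0.950·0.975 = 7.4% |

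The comparator is 2.5% for one test. At the protocol's vehicle rate the four subgroup tests together stay within 2.5%, because exact tests in small strata run well below their nominal level. The %BSA test brings the total to 4-5%.

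**Failed primary alongside a significant subgroup when the effect is real (60 per arm).** These are not false-positive rates.

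- True 25% v 12% (an assumption), latent correlation 0.6: 10.6 fails in 82.5% of trials, and 35.6% of those failures have at least one significant subgroup test. Near full correlation the second figure is about 17%.
- True 40% v 12% (the protocol's rates): failure of 10.6 together with a significant subgroup occurs in about 3.5% of all trials near full correlation, and in about 10% at 0.6.

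**After the fix, with no true effect.** Any secondary superiority statement first requires both co-primaries to win. Its probability is therefore at most 0.025² = 0.06% at zero correlation and 2.5% at full correlation. A superiority statement after a failed primary has probability 0.

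**The case against.** The strongest objection is that the protocol keeps the two kinds of claim apart. Only 10.6 lets superiority be *demonstrated*; 10.7 says *supported*, and only per endpoint. A reader might infer that a failed trial could still claim superiority overall, or that the subgroup tests are four extra chances at the primary claim. The text supports neither reading. No secondary result can satisfy 10.6, and the type I error of the overall claim is not inflated because both co-primaries must be significant. This part of the objection stands in full.

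The size of the problem is also easily overstated. The four subgroup tests add almost nothing at a 12% null rate, the 7.4% needs a null response equal to the protocol's active-arm rate, and 11.9% requires independent full-level tests. The 25% v 12% scenario contains a true effect, so its subgroup wins are not false claims. These corrections stand too and are built into the figures above.

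Finally, the lack of adjustment is openly stated, and the SAP, which is not at hand, could add a gate. Disclosure does let a reader discount the p-values. But 10.7 itself fixes an unconditional per-endpoint superiority rule, so this is a stated rule and not a detail left open. A gate placed only in the SAP would leave the protocol saying something different.

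**Conclusion.** The point holds as a weakness in how secondary claims are worded and controlled, not as a threat to the primary conclusion. As written, a trial that misses 10.6 may still report endpoint-level or subgroup-level superiority as supported, and error across the five statements is uncontrolled.

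The excess is modest: about 4-5% at a 12% response rate and up to about 7.5% at 40%, against 2.5% for a single test, with 11.9% only as an outer bound. These figures rest on the assumed even IGA split, the assumed correlations, the independent %BSA test and Fisher's test. The change is worth making because it costs little and removes the possibility of a superiority statement after a failed primary.

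**What to change.** State in 10.7 and in the synopsis that:

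- secondary endpoints are assessed for superiority only if both co-primaries are significant under 10.6;
- they are then tested in a pre-specified fixed order (for example the order listed in 10.5), each at two-sided 5%, stopping at the first non-significant result;
- if 10.6 is not met, and for endpoints after the stopping point, estimates and nominal p-values are reported with no superiority statement.

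Replace the no-adjustment sentence accordingly, and fix the order before unblinding. This is a wording change only, with no effect on sample size, endpoints or conduct. The cost is that an endpoint low in the order may be reported only as nominal even when its own p-value is below 0.05.

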### **10.8 Treatment-by-Site Interaction and Pooling of Clinical Sites**

As this is a multiple-site study, the interaction of treatment-by-site may be evaluated for superiority testing by the Breslow-Day test for homogeneity of the odds ratio at the 5% significance level ( $p < 0.05$ ) for the primary efficacy endpoints in the ITT population. A site(s) with a low enrollment rate(s) may be pooled with its geographically closest site, so as to avoid bias in the estimation of a treatment-by-site interaction effect. The pooling will be done for low enrolling sites that account for less than 4-7% of the total number of patients at the site with the highest enrolling rate in the ITT population. If no treatment-by-site interaction is identified with the primary endpoints then no adjustment will be made to any efficacy analysis and treatment-by site interaction will not be included as a term in the statistical models for evaluating superiority.

### **10.9 Safety Analysis**

Adverse events (AEs) will be classified using standard MedDRA terminology Version 17.0 or higher and summarized by treatment group. Summary tables comparing the type, incidence, severity will be prepared by treatment group. The relationship of AEs, if any, to the study drug will be assessed by the Investigator. All AEs will be presented

## **CONFIDENTIAL PROTOCOL**

A Randomized, Double-Blind, Placebo-Controlled, Parallel-Design, Multiple-Site Clinical Study to Evaluate the Efficacy and Safety of Desoximetasone Topical Spray, 0.15% (Taro Pharmaceuticals, U.S.A., Inc.) in Patients with Mild to Moderate Plaque Psoriasis

---

regardless of suspected causality. The frequency, severity and relationship to study drug for AEs in each treatment group will be used to evaluate the safety profile of the test product.

### **11.0 REGULATORY OBLIGATIONS**

#### **11.1 Institutional Review Board**

The study protocol, informed consent/assent form, Investigator's Brochure, or package insert (as applicable), and any specific advertising will be submitted to, and approved by, an Institutional Review Board (IRB) before the start of the study. A form must be signed by the chairman or designee of the IRB noting the approvals. This notification of the board's approval along with a description by profession and gender of the board's composition will be provided to the Sponsor.

#### **11.2 Study Documentation**

This study will be conducted in compliance with the protocol, Good Clinical Practices (GCPs) and all applicable regulations, including the Federal Food, Drug and Cosmetics Act, US applicable Code of Federal Regulations (title 21), parts 50, 56, 312, 320 and any IRB requirements relative to clinical studies and the Declaration of Helsinki, June 1964, as modified by the 59th World Medical Association General Assembly, October 2008. The Investigator will permit trial-related monitoring, audits, IRB review and regulatory inspections providing direct access to source data/documents.

##### **11.2.1 Protocol**

The Investigator indicated on FDA Form 1572 will act as the Principal Investigator at each study site. Protocols will be noted as approved by placement of the Novum Representative's signature on the cover page. The Sponsor of the study will also approve the protocol by having a study-responsible individual sign the protocol cover page.

##### **11.2.2 Informed Consent**

An Informed Consent Form (ICF) that includes all of the relevant elements currently required by FDA and local State regulations will be provided to each prospective study patient before enrollment into the study. The type and method of study, tests to be administered, any potential or possible hazards, and the patient's right to withdraw from the study at any time will be explained to the patients by the Investigator or designee. Once the Investigator or designee is assured that an individual candidate understands the implications of participating in this study, the patient will be asked to give consent by signing and dating in the appropriate areas of the ICF. The Investigator or designee will also sign and date the form, along with a staff member who will sign the ICF as a witness to verify that the patient has indeed received information. For illiterate patients, verbal consent should be obtained in the presence of and be countersigned by a

## **CONFIDENTIAL PROTOCOL**

A Randomized, Double-Blind, Placebo-Controlled, Parallel-Design, Multiple-Site Clinical Study to Evaluate the Efficacy and Safety of Desoximetasone Topical Spray, 0.15% (Taro Pharmaceuticals, U.S.A., Inc.) in Patients with Mild to Moderate Plaque Psoriasis

---

literate witness. If any other language is required, translation will be performed by a certified translator. A copy of the ICF will be provided to the patient.

### **11.2.3 Protocol and Informed Consent Changes**

Revisions to the original protocol will be documented in amendments, incorporated as a preface to the new version and approved by the IRB. Any revision that substantially alters the study design or increases potential risk to the patient requires the patient's consent to continue in the study. Revisions to the original ICF will also be approved by the IRB. The approvals will be processed in accordance with the established IRB procedures. Copies of all protocol and ICF amendments/revisions, along with letters noting IRB approval, will be submitted to the Sponsor.

### **11.2.4 Source Documents and Case Report Forms**

All patients will be identified by initials, date of birth, and a unique patient number. Source documents will be used to record all study-related data. Source document entries will be used to complete Case Report Forms (CRFs). A set of CRFs will be completed for each patient enrolled in the study. All data and CRFs will be reviewed, evaluated and signed by the Investigator, as required.

The original source documents and a copy of the corresponding CRFs will be retained by the Investigator. Patients who terminate early from the study will have the Visit 4 (end of treatment) source/CRF completed.

### **11.2.5 Drug Accountability**

All drug receipt, inventory, dispensing, dosing and reconciliation records will be maintained in compliance with Federal Regulations. The study drug will be dispensed to qualified study patients according to established procedures. At the end of the study (after the database has been locked) all used and unused study medication will be returned to Sponsor or designee.

### **11.2.6 Drug Storage**

All study medication will be stored at controlled room temperature 15-30°C (59-86°F), in a secure place with access by authorized individuals only. The Investigator will be responsible for maintaining accurate records of drug receipt, dispensing, and return. At the end of the study, all partially used and unused study medication will be returned to Sponsor or designee.

### **11.2.7 Pregnancies**

Patients with a positive pregnancy test during screening will not be enrolled in the study. Patients who report that they have become pregnant during the study or have a positive pregnancy test at Visit 4 will be followed to completion of the pregnancy. The pregnancy will be reported as an AE.

## **CONFIDENTIAL PROTOCOL**

A Randomized, Double-Blind, Placebo-Controlled, Parallel-Design, Multiple-Site Clinical Study to Evaluate the Efficacy and Safety of Desoximetasone Topical Spray, 0.15% (Taro Pharmaceuticals, U.S.A., Inc.) in Patients with Mild to Moderate Plaque Psoriasis

---

Female patients of childbearing potential must have been using and must agree to continue to use accepted methods of birth control, throughout the study. All female patients are considered to be of childbearing potential unless they are premenarchal, have been surgically sterilized or have been postmenopausal for at least 1 year. Abstinence is an accepted method of birth control. Alternatively, any of the following methods of birth control are acceptable: oral contraceptives, contraceptive patches/implants (e.g., Norplant®), Depo-Provera®, double barrier methods (e.g., condom and spermicide) or IUD. Before study enrollment women of child bearing potential must be advised of the importance of avoiding pregnancy during study participation.

A negative result of a urine pregnancy test having a minimum sensitivity of at least 25 mIU/ml for hCG should be obtained, before study participation. Pregnancy testing will be performed at Visits 1 and 4 and the results of all pregnancy tests (positive or negative) will be documented.

If following initiation of study treatment, it is subsequently discovered that a study patient is pregnant or may have been pregnant at the time of study product exposure, the study product will be permanently discontinued. The Principal Investigator must immediately notify the Medical Monitor of this event.

Protocol-required procedures for study discontinuation and follow-up must be performed on the patient. Other appropriate pregnancy follow-up procedures should be considered if indicated. In addition, the Principal Investigator must report to the sponsor follow-up information regarding the course of the pregnancy, including perinatal and neonatal outcome. Infants should be followed for a minimum of eight weeks after birth.

### **11.2.8 Reporting Safety Information to the IRB**

The Investigator must promptly report to the Investigator's IRB all unanticipated problems involving risks to patients. This includes death from any cause and all serious adverse events occurring during the study, regardless of the assessed causality.

### **11.2.9 Record Retention**

All drug accountability records, CRFs, source data and related regulatory documents must be retained for at least ten years following completion of the study or for two years after the test product has been approved for marketing by the Food and Drug Administration.

### **11.2.10 Study Monitoring and Auditing**

Novum will be responsible for monitoring the study according to Good Clinical Practice and applicable regulations. Monitoring visits are for the purpose of confirming adherence to the protocol and to verify complete and accurate data

## **CONFIDENTIAL PROTOCOL**

A Randomized, Double-Blind, Placebo-Controlled, Parallel-Design, Multiple-Site Clinical Study to Evaluate the Efficacy and Safety of Desoximetasone Topical Spray, 0.15% (Taro Pharmaceuticals, U.S.A., Inc.) in Patients with Mild to Moderate Plaque Psoriasis

---

collection. The clinical site will make all records associated with the study available to Novum's representative during such visits and audits

The study may be subject to audit by the Sponsor, Sponsor Representative or by regulatory authorities. If such an audit occurs the Investigator must agree to allow access to required patient records. By signing this protocol, the Investigator grants permission to personnel from the Sponsor, its representatives and appropriate regulatory authorities for on-site monitoring of all appropriate study documentation, as well as on-site review of study procedures.

